6.1.4 Short term follow up (q4 week visits x3 following Efficacy/Scan visit)

Unless subjects withdraw or initiate new treatment, the following procedures must be completed every 4 weeks (+/- 7 days) after the scan visit:

- Targeted Physical Examination with vital signs and weight
- Interim Medical History
- ECOG Performance Status
- CBC with differential and platelet count
- CMP (with direct bilirubin with known Gilbert's syndrome)

- PSA
- LDH

These visits may be performed with any licensed provider at any CLIA certified lab, provided that the results are available/provided to the Investigator within allowable windows. Repeat CT and bone scan are recommended with the final short-term follow up visit (approx. 6 months after enrollment).

6.1.5 Progression

If a subject will not initiate a new treatment, then progression is considered to be by PCWG3 radiographic progression or clinical progression. However, if a subject has PSA progression and will initiate a new systemic therapy, then progression procedures should be performed prior to starting new therapy. Any procedure already performed for another visit within 2 weeks of the progression visit does not need to be repeated.

The following procedures must be completed during the progression visit:

- Targeted Physical Examination with vital signs and weight
- Medical History
- Brief Pain Inventory, FACT-P
- ECOG Performance Status
- CBC with differential and platelet count
- CMP (with direct bilirubin with known Gilbert's syndrome)
- PSA
- LDH
- Testosterone
- Cell-Free DNA BCT® Research blood sample
- Immune research blood sample
- Adverse event evaluation
- Concomitant medications
- Concomitant procedures

6.1.6 Long Term Follow Up

Survival assessment and relevant medical history to be collected until death. Information may be collected from external providers.

Per PCWG3, we recommend follow up CT and bone scans q12 weeks until radiographic progression

6.2. Treatment Administration

6.2.1. Agent Administration

Treatment will be administered only to eligible subjects under the supervision of the investigator or identified co-investigator(s). Treatment will be administered on an outpatient basis. Reported adverse events and potential risks are described in Section 13. Appropriate dose modifications/delays of the study drug are described in Section 7. No investigational or commercial agents or therapies other than those described below may be administered with the intent to treat the subject's malignancy.

6.2.2. Study drug preparation

[REDACTED] produces both peptides/ligands, PSMA-HBED-CC and PSMA-617. Upon purchase and shipment to Weill Cornell Medicine, they will be labeled with either ^{68}Ga or ^{177}Lu with final products being ^{68}Ga -PSMA-HBED-CC and ^{177}Lu -PSMA-617, respectively. Radionuclide conjugation will be done at the Division of Nuclear Medicine, Department of Radiology, Weill Cornell Medicine.

The material produced are subjected to quality assurance testing as outlined in the Food and Drug Administration "Points to Consider". All production data and supporting documents, together with the results of all quality assurance testing, have been provided to and reviewed by the Food and Drug Administration (^{68}Ga -PSMA-HBED-CC, IND# 124495 and ^{177}Lu -PSMA-617, IND # 131966).

6.2.3. Route of Administration

^{68}Ga -PSMA-HBED-CC and ^{177}Lu -PSMA-617 will be administered as an intravenous infusion.

6.2.4. Dose levels for ^{177}Lu -PSMA-617

Subject(s) enrollment will be done as 3+3 study design at each dose level. Initially at least 3 subject(s) will be enrolled in Cohort 1 (100 mCi or 3.7 GBq x2 doses 2 weeks apart) with dose escalation (or de-escalation as described above in Section 4 / Table 7).. The enrollment ceiling of the dose escalation portion of the study is up to 46 study participants (six groups, with 3+3 at each dose level). Additional 10 subjects will be enrolled at the MTD dose level to further assess safety and tolerability and to obtain a preliminary assessment of efficacy. Each patient would receive 2 doses of the investigational agent, 2 weeks apart. The total dose received in 2 treatments in phase 1 will be 100 – 600 mCi or 3.7 – 22.2 GBq. The total dose for phase 2 is 600 mCi (22.2 GBq).

6.2.5. Dose levels for ^{68}Ga -PSMA-HBED-CC

All subjects enrolled will receive **5 \pm 2mCi or 185 \pm 74MBq** of ^{68}Ga -PSMA-HBED-CC during the screening visit and EOS visit.

6.2.6. Study drug premedication

No pre-medication is required. Individual subjects may receive pre-medication at the discretion of their treating physician provided that they are not prohibited medications per study.

6.2.7. Study drug administration

Intravenous access must be well established prior to initiating infusion. At the time of dosing, the IV line will be connected to an infusion container containing the prepared volume of ^{68}Ga -PSMA-HBED-CC or ^{177}Lu -PSMA-617.

6.2.8. Monitoring Vital signs pre/post ^{68}Ga -PSMA-HBED-CC or ^{177}Lu -PSMA-617 infusion

The infusion of ^{177}Lu -PSMA-617 and subsequent monitoring will occur in a facility that is equipped for cardio-pulmonary resuscitation. The dispensed dose will be infused under the supervision of nuclear medicine physician or designee under the supervision of a nuclear medicine physician. Infusion-related reactions (fever, rigors) will be treated with acetaminophen, meperidine and diphenhydramine hydrochloride as clinically appropriate. Other allergic events will be managed as follows: rash, pruritus, urticaria and wheezing will be treated with diphenhydramine hydrochloride, meperidine and/or steroids as clinically appropriate. Anaphylaxis or anaphylactoid signs or symptoms will be treated with steroids and/or epinephrine as clinically indicated. Vital signs will be monitored during the infusion. Systolic and diastolic blood pressure (mm Hg), temperature, pulse rate (beats/minute), and respiratory rate (breaths/minute), will be recorded with the patient in sitting position. Any clinically significant change in the vital signs will be recorded as AEs. Serial vital signs including temperature, BP, and heart rate will be monitored within 30 minutes before the infusion, within 30 minutes and at 60 minutes (+/-10) after the infusion. If any subject has any adverse reaction at 60 minutes, they will stay longer until it is resolved.

6.2.9. Imaging Plan

A. ^{68}Ga -PSMA-HBED-CC PET/CT Scan

Patient preparation should be according to the policies and procedures of the local imaging site (CIBC). The patient does not need to be fasting for either the infusion or

the scans. The use of intravenous or oral contrast will not be permitted. Specifications for acquiring the ⁶⁸Ga-PSMA-HBED-CC PET/CT scans will be provided in study specific documentation by the study chair or the co-investigators from the Division of Nuclear Medicine. PET/CT should be obtained during the Screening Visit as well as at the end of study visit. The images are acquired between 1 and 3 hours after the ⁶⁸Ga-PSMA-HBED-CC infusion. Image acquisition will be from vertex of skull to mid thighs.

B. ¹⁷⁷Lu-PSMA-617 Planar/SPECT imaging

Patient preparation should be according to the policies and procedures of the local imaging site (CIBC). The patient does not need to be fasting for either the infusion or the scans. The use of intravenous or oral contrast will not be permitted. Specifications for acquiring the ¹⁷⁷Lu-PSMA-617 planar/SPECT images will be provided in study specific documentation by the study chair or the co-investigators from the Division of Nuclear Medicine. Planar/SPECT images should be obtained during the Imaging Visit (Day 8 ±1) on all subjects after the ¹⁷⁷Lu-PSMA-617 infusion. Image acquisition will be from vertex of skull to mid thighs. Optional images will be performed on selected consenting subjects between initial Treatment Visit (between D1 - D4) and prior to Treatment Visit 2 (Day 15 ±1).

Managing toxicity

NCI CTCAE version 4.0 is used to grade all adverse events.

- Grade ≥ 2 thrombocytopenia or neutropenia within 24 hours of the second dose of ¹⁷⁷Lu-PSMA-617 (Treatment Visit 2) requires a subject's treatment to be held until the toxicity has resolved to least grade 1. If the toxicity has not resolved after 2 weeks of monitoring, the subject's ¹⁷⁷Lu-PSMA-617 treatment will be permanently discontinued and will be termed dose-limiting toxicity.

Dose-limiting toxicity (DLT) is defined as:

- Grade 4 hematologic toxicity that is deemed at least possibly related to ¹⁷⁷Lu-PSMA-617 will be termed dose-limiting toxicity.
- Any grade > 2 non-hematologic toxicity deemed to be at least possibly related to ¹⁷⁷Lu-PSMA-617 will require a subject's ¹⁷⁷Lu-PSMA-617 treatment to be permanently discontinued and will be termed dose-limiting toxicity.

Maximum Tolerated Dose (MTD) is defined as:

- The dose that produces an "acceptable" level of toxicity or that, if exceeded, would put subjects at "unacceptable" risk for toxicity. Definition of the MTD

usually relies on the sample, as MTD is defined as the dose level at which more than two patients over six experienced dose-limiting toxicity (DLT).

Note: toxicities as described above will be considered DLT if they are at least possibly related to ⁶⁸Ga-PSMA-HBED-CC or ¹⁷⁷Lu-PSMA-617 as judged by the investigator. Attribution will be reviewed by the study chair and discussed with the medical monitor if there are questions about severity or attribution.

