Cohort	Treatment Dose mCi (GBq)		Total mCi (Dose GBq)	Subjects (n)
	Day 1	Day 15			
-1	50 (1.85)	50 (1.85)	100 (3.7)	1-6
1	100 (3.7)	100 (3.7)	200 (7.4)	1-6
2	150 (5.55)	150 (5.55)	300 (11.1)	1-6
3	200 (7.4)	200 (7.4)	400 (14.8)	3-6
4	250 (9.25)	250 (9.25)	500 (18.5)	3-6
5	300 (11.1)	300 (11.1)	600 (22.2)	3-6

4.2 Rationale for Dose-Escalation Strategy:

This study will use a modified phase I 3+3 dose-escalation study design, with the planned initial and subsequent cohorts described in Table 7. This study design is well-described and accepted by the clinical and scientific community, so we will not provide complete details here. Briefly, this design is constructed to reduce the chance of escalating the dose when the probability of DLT is high, and increase the chance of escalating the dose when the probability of DLT is low. Given the fact that some pre-existing clinical efficacy and toxicity data exists with the study drug, we will allow up to 6 subjects to be treated at a given dose-level even in the absence of DLT. The MTD is defined as the highest dose level with an observed incidence of DLT in no more than one out of six patients treated at a particular dose level. The dose escalation scheme provides the following probabilities of escalation based on the true chances of DLT at a specific dose level. One can see that the probability of escalation is high if the toxicity risks are low:

True Probability of Toxicity:	.05	.10	.20	.30	.40	.50	.60
Probability of Escalation:	.97	.91	.71	.49	.31	.17	.08

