12. STATISTICAL CONSIDERATIONS

12.1. Study Design/Endpoints

This is a phase 1 study of subjects with documented progressive metastatic CRPC with the primary endpoint of determination of MTD (or recommended phase II dose). In general, if there are sufficient numbers of subjects, descriptive statistics (e.g., number of observations, means, standard deviations, medians, and ranges) will be used to summarize data and selected endpoints may be summarized by dosing regimen. Otherwise, subject listings will be provided. No formal hypothesis testing is planned.

The dose-escalation schedule (using 3+3 modified Fibonacci escalation), definitions of DLT, and determination of MTD are defined above (Section 6.2.10). The design is constructed to reduce the chance of escalating the dose when the probability of DLT is high, and increase the chance of escalating the dose when the probability of DLT is low. The maximum tolerated dose is defined as the highest dose level with an observed incidence of DLT in no more than one out of six patients treated at a particular dose level. The dose escalation scheme provides the following probabilities of escalation based on the true chances of DLT at a specific dose level. One can see that the probability of escalation is high if the toxicity risks are low.

True Probability of Toxicity	0.05	0.10	0.20	0.30	0.40	0.50	0.60
Probability of Escalation	0.97	0.91	0.71	0.49	0.31	0.17	0.08

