12.5. Analysis of Endpoints

12.5.1. Analysis of Primary Endpoints

The primary endpoint will be the proportion of subjects with DLT from Treatment Visit 1 through **Efficacy/Scan Visit**. The MTD is the highest dose amongst the different dose-level cohorts in this study at which no more than 2 (33%) of the subjects in a cohort experience DLT.

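### The MTD, a phase I primary endpoint, has three incompatible definitions: at most 1 DLT in 6, at most 2 (33%), and more than 2 in 6

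*Combined protocol and SAP*

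**What the plan says.** Four places in the current protocol define the MTD, and they give three different rules.

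- **Sections 4.2 and 12.1:** the MTD is the "highest dose level with an observed incidence of DLT in no more than one out of six patients". Both sections attach the same table of escalation probabilities.
- **Section 12.5.1 (Analysis of Primary Endpoints):** the MTD is the highest dose "at which no more than 2 (33%) of the subjects in a cohort experience DLT".
- **Managing toxicity:** "MTD is defined as the dose level at which more than two patients over six experienced dose-limiting toxicity (DLT". This heading has no number in the body; the table of contents lists it as 6.2.10.

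Section 12.1 says that the "definitions of DLT, and determination of MTD are defined above (Section 6.2.10"), and then in the same paragraph states the one-in-six rule. No section says which definition governs.

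Two other statements matter here. Section 4.2 adds to the usual 3+3 that "we will allow up to 6 subjects to be treated at a given dose-level even in the absence of DLT". Section 6.2.4 fixes the later dose: "The total dose for phase 2 is 600 mCi (22.2 GBq").

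**The concern.** Section 12.1 names determination of the MTD (or recommended phase II dose) as the phase I primary endpoint, and section 1.1 lists it as a primary objective. A dose-finding trial needs one decision threshold, fixed before the DLT counts are known. Here an analyst who follows section 12.5.1 and one who follows section 12.1 can report different MTDs from the same data.

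Read literally, the Managing toxicity clause is worse. It attaches the MTD label to a level with at least 3 DLTs in 6 (50% or more), which both other rules reject. It also contradicts its own lead-in, which describes the MTD as a dose with acceptable toxicity.

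The label has some use beyond reporting. Sections 4.2 and 12.2 count the 3 to 6 patients used to establish the MTD towards the 27 in phase II. If 600 mCi produced 2 DLTs in 6, sections 4.2 and 12.1 would place the MTD below the phase II dose, whereas section 12.5.1 would place it at the phase II dose.

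**Working it through.** **Inputs.** The three MTD rules are those set out above. The printed escalation probabilities (sections 4.2 and 12.1) are 0.97, 0.91, 0.71, 0.49, 0.31, 0.17 and 0.08 at true DLT rates *p* of 0.05, 0.10, 0.20, 0.30, 0.40, 0.50 and 0.60.

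**Step 1: reproduce the printed row.** In the standard 3+3, a level passes on 0/3, or on 1/3 followed by 0/3 (at most 1/6):

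P(pass, ≤1/6) = (1−p)³ + 3p(1−p)² × (1−p)³ = (1−p)³ + 3p(1−p)⁵

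At p = 0.30: 0.343 + 0.9 × 0.16807 = 0.343 + 0.151 = 0.494. All seven values round to the printed row (table below).

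**Step 2: the disputed outcome.** For a completed six-patient level, ≤1/6 and ≤2/6 disagree only at exactly 2 DLTs. When expansion follows only 1/3, the path is 1/3 then 1/3:

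P(1/3 then 1/3) = [3p(1−p)²]² = 9p²(1−p)⁴

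At p = 0.30: 9 × 0.09 × 0.2401 = 0.194.

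**Step 3: pass probability under ≤2/6.** This is the sum of steps 1 and 2. At p = 0.30: 0.494 + 0.194 = 0.689, from unrounded terms.

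| True DLT rate | Printed | ≤1/6 (step 1) | 1/3 then 1/3 (step 2) | ≤2/6 (step 3) |
|---|---|---|---|---|
| 0.05 | 0.97 | 0.973 | 0.018 | 0.992 |
| 0.10 | 0.91 | 0.906 | 0.059 | 0.965 |
| 0.20 | 0.71 | 0.709 | 0.147 | 0.856 |
| 0.30 | 0.49 | 0.494 | 0.194 | 0.689 |
| 0.40 | 0.31 | 0.309 | 0.187 | 0.496 |
| 0.50 | 0.17 | 0.172 | 0.141 | 0.313 |
| 0.60 | 0.08 | 0.082 | 0.083 | 0.165 |

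**Step 4: sensitivity to how cohorts are filled.**

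- If a level is also expanded after 2/3, the ≤2/6 rule gains 3p²(1−p) × (1−p)³ = 3p²(1−p)⁴. The pass probabilities become 0.905, 0.754 and 0.558 at p = 0.20, 0.30 and 0.40, which is further from the printed row.
- If six patients are always treated, which section 4.2 permits but does not require, the chance of exactly 2 DLTs is 15p²(1−p)⁴ = 0.246, 0.324 and 0.311 at the same three rates. The ≤1/6 rule then passes with probability 0.655, 0.420 and 0.233, and ≤2/6 with 0.901, 0.744 and 0.544.

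Of these schemes, only the standard 3+3 with ≤1/6 gives the printed row.

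**Step 5: smaller cohorts.** Table 7 allows levels with fewer than six patients. There, section 12.5.1 also disagrees with itself: 2 of 3 is 67%, not 33%.

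**The case against.** The strongest reply is that the intended rule can be recovered from the text. The Managing toxicity clause is generic wording after a correct lead-in, and no trialist would declare a dose with three or more DLTs in six tolerated. Section 12.1 cites that section but then states the one-in-six rule itself, with a table that fits it, and section 4.2 repeats both. I accept that the clause is probably a slip. Setting it aside still leaves one in six against two in six, and the outlying threshold sits in the section headed as the primary-endpoint analysis.

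The consequence is also narrow. Sections 1.1 and 12.1 allow a recommended phase II dose as an alternative to the MTD, and phase II is fixed at 600 mCi, the top planned level. The rules diverge only if a decisive level had exactly 2 DLTs in 6, and the documents give no DLT counts. This stands and limits the effect mainly to determination and reporting.

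Two points about the figures also stand. At true DLT rates of 5% and 10% the disputed outcome is uncommon (0.018 and 0.059), and section 2.5 reports no attributable grade 4 toxicity in earlier use of this drug class. Section 12.5.1 states an MTD definition and not an escalation rule, so the ≤2/6 pass column shows what that threshold would mean if it governed whether a level passes. Neither point removes the conflict.

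**Conclusion.** The concern holds and should be fixed; it does not invalidate the trial. The text gives three incompatible MTD rules for a phase I primary endpoint and no order of precedence. The rule whose operating characteristics the plan prints is at most 1 DLT in 6.

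The working conflict, 2 DLTs in 6, has probability 0.15 to 0.19 at true DLT rates of 20% to 40% when expansion follows only 1/3. It is 0.25 to 0.32 if six are always treated. At a true 40% rate, moving from ≤1/6 to ≤2/6 raises the chance of passing from 0.31 to 0.50. These figures assume independent DLTs with a common rate within a level.

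If 600 mCi had 0 or 1 DLT in 6, the ≤1/6 and ≤2/6 rules give the same MTD. If it had 2 in 6, the MTD is 600 mCi under section 12.5.1 and a lower level under sections 4.2 and 12.1. Which case applies cannot be known from the documents.

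**What to change.** Use one definition throughout: the highest dose level at which no more than one of six patients has a DLT. It is already stated twice and is the rule behind the printed table. Two sentences change:

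- **Managing toxicity (6.2.10):** replace the more-than-two-of-six clause with this definition.
- **Section 12.5.1:** replace the threshold of 2 (33%) with the same definition.

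The printed escalation table can stay. It is exact for the 3+3 that expands only after 1/3, and a short note saying so would cover the option in section 4.2 to treat six without DLT.

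If the sponsor prefers at most 2 in 6, sections 4.2, 12.1 and 6.2.10 must change instead, and the table must be recomputed. With expansion only after 1/3 the row would read 0.99, 0.97, 0.86, 0.69, 0.50, 0.31 and 0.17.

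The recommended option costs two corrected sentences, with no added patients and no new table.

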6.3. General Concomitant Medication and Supportive Care Guidelines

All medications that are administered during the study must be recorded in the patient's CRF and in the source documents. Concomitant medications for other medical conditions are permitted as clinically indicated subject to approval by the study chair.

Subjects will be advised to use contraceptive precautions to avoid pregnancy during the treatment phase since the effects of investigational agents on sperms and embryos are unknown.

6.4. Duration of Therapy and Criteria for Removal from Study

Duration of treatment portion of the study (excluding screening time) will be approximately 85 Days (± 7 days). By signing the informed consent form and agreeing to participate in this study, the subjects are required to participate in entirety up to the completion of all scheduled visits and study procedures, or until one of the following criteria applies:

- A protocol violation occurs
- Disease progression occurs
- A serious or intolerable adverse event occurs (that in the opinion of the Investigator, requires the subject's discontinuation)
- The Investigator withdraws the subject (at the Investigator's discretion for reasons other than the adverse event)
- The Principle Investigator terminates the protocol
- The subject requests to be discontinued from the protocol
- The subject is lost to follow-up
- Intercurrent illness that prevents administration of ⁶⁸Ga-PSMA-HBED-CC or ¹⁷⁷Lu- PSMA-617
- Previous anaphylactic reaction to PSMA peptides/ligands

The investigators or physicians may stop the protocol or terminate a subject's participation in the protocol at any time should they judge:

- That it is not in the subject's best interest to continue
- If the subject experiences a protocol-related injury
- If the subject needs life-saving medications/procedures/treatment
- If the subject does not comply with the study plan
- General or specific changes in the patient's condition render the patient unacceptable for further treatment in the judgment of the investigator

They may also remove the subject from the study for various other administrative and medical reasons. They can do this without the patient's consent.

6.5. Duration of Follow Up

Patients will be followed until death for survival assessment. Patients removed from study for unacceptable adverse events will be followed until resolution or stabilization of the adverse event.

8. DOSING DELAYS/DOSE MODIFICATIONS

There will be no dosing modifications. Unless there are specific reasons not to do so, all patients who are eligible for the trial will receive 5 ± 2 mCi (185 ± 74 MBq) of ^{68}Ga - PSMA-HBED-CC during the Screening Visit and the Efficacy/Scan visit. During the treatment phase, the subject will receive ^{177}Lu -PSMA-617 x 2 doses based on the dose-level/Cohort to which he is assigned. The study chair must clear any dosing delays due to logistical issues (e.g. subject scheduling and/or radionuclide shipping that fall outside of a 2-day window).

9. PHARMACEUTICAL INFORMATION

A list of the adverse events and potential risks associated with *Investigational Agent* can be found in Section 13.

9.1. Investigational Agent

PSMA-617 and PSMA-HBED-CC were initially purchased from [REDACTED] [REDACTED] and in the later part of the study PSMA-617 will be provided by [REDACTED] Lignads will be shipped to and stored at WCM as per manufacturer's guidelines. Upon subject's enrollment and confirmation of date of infusions, these peptides will be labeled with Lutetium-177 or Gallium-68 respectively.

The material produced are subjected to quality assurance testing as outlined in the Food and Drug Administration "Points to Consider". All production data and

supporting documents, together with the results of all quality assurance testing, have been provided to and reviewed by the Food and Drug Administration.

